9.4.6 Blinding

The study will be conducted as a double-blind investigation. A list of patient randomization codes will be generated by the Sponsor's Statistical Programming, and implemented by the IxRS vendor (an electronic version will be stored on a secure server). This list will identify each patient by randomization number and include the patient's corresponding treatment assignment.

9.4.7 Unblinding

Any unblinding at the study center level should be done only in an emergency that requires for the investigational product to be identified for the medical management of the patient. The Investigator has to notify the study physician immediately (see Appendix II) and a full written explanation must be provided if the blind is broken. Before the investigational product is unblinded, every attempt should be made to discuss the case with the Study Physician. Breaking the code at the study center will immediately disqualify the patient from further participation in the study.

Treatment codes may be broken by the Sponsor's Global Drug Safety department, for regulatory reporting purposes. In such cases, the study staff will be kept blinded and the patient will not need to be disqualified from the study.

In an emergency, the Investigator can obtain the treatment assignment of any patient at his or her study site through the IxRS. In an emergency, the Investigator will access the IxRS to break the blind.

The unblinding of bioanalytical representatives is to be carried out in a secure manner following the Sponsor's standard operating procedures. Extreme care and diligence will be taken to ensure no other individuals outside the bioanalytical team will be unblinded.

9.4.8 Prior and Concomitant Therapy

A complete list of drugs that are allowed and not allowed as concomitant medications for either episodic or long-term use is provided in Appendix III. Throughout the duration of this study, additional psychotropic medications, including psychostimulants, are not allowed, with some notable exceptions listed below. Psychotropic medications include the following: antipsychotics, antidepressants (including monoamine oxidase-B inhibitors), stimulants, anticonvulsants/mood stabilizers, sedatives/hypnotics/anxiolytics, dopamine releasing drugs or dopamine agonists, and psychotropic drugs not otherwise specified (including herbal products).

Patients will be asked to abstain from drinking alcohol during the study. Patients who have been taking stable doses of benzodiazepines (up to 2 mg/day) for at least 1 month before randomization can continue use. Medically appropriate episodic use (up to 3 days) of narcotic analgesics for acute medical indications (i.e., tooth extraction) is allowed during the study.

Medication history, including the use of psychotropic medication and of any other medication, will be recorded at Visit 1 (Screening). Thereafter, any changes in concomitant medications or new medications added will be recorded in the eCRF.

For insomnia the following will be allowed. It should not be prescribed prophylactically.

- Zolpidem (maximum of 10 mg/day)
- Zolpidem extended release (maximum of 12.5 mg/day)
- Zaleplon (maximum of 20 mg/day)
- Eszopiclone (maximum of 3 mg/day)
- Zopiclone (maximum of 7.5 mg/day)
- Chloral hydrate (maximum of 1000 mg/day) may be used acutely with approval from Study Physician)

These medications must be administered before bedtime as recommended in their prescribing information. The medication must be documented on the concomitant medications page of the eCRF. No such medication is permitted within 8 hours of psychiatric or neurological assessments.

For EPSs or akathisia:

For EPSs or akathisia that emerge or worsen during the study, the following rescue medications will be allowed; however, each of the 3 EPS scales (Abnormal Involuntary Movement Scale [AIMS], Barnes Akathisia Rating Scale [BARS], and Simpson Angus Scale [SAS]) should first be performed (unless a medical urgency [eg, dystonia, severe akathisia, etc] requires otherwise) to support the decision to administer the medications:

- Benztropine (up to 4 mg/day orally or up to 2 mg/day if given parenterally) or equivalent (eg, trihexyphenidyl up to 6 mg/day in divided doses)
- Diphenhydramine (up to 50 mg/day) for EPS
- Propranolol for the treatment of akathisia. Daily dose of propranolol depends on heart rate and BP (up to 160 mg/day)

The medication listed above should not be used prophylactically. The need for continued use of these medications should be regularly assessed by the PI and documented appropriately. The EPSs must be documented on the AE page of the eCRF, and the medication on the concomitant medications page of the eCRF.

Injectable agents are not allowed, except for the treatment of an acute dystonic reaction if deemed necessary.

Rescue medications for agitation, restlessness, and hostility:

Episodic use of lorazepam up to 2 mg/day (or equivalent) and for up to 3 consecutive days at a time is allowed for agitation, restlessness, and hostility.

The agitation, restlessness, or hostility must be documented on the AE and/or the medical history page of the eCRF. The medication use must be documented on the rescue medication page of the eCRF. Efficacy assessments should not be performed within 8 hours of administration of lorazepam or equivalent benzodiazepine or within 24 hours of administration of diazepam.

9.4.9 Monitoring Treatment Compliance

Investigational product compliance will be monitored by counting the number of capsules dispensed and the number returned by the patient. Before new investigational product is dispensed at any visit, every effort will be made to collect all unused investigational product. If a patient demonstrates poor compliance at any time during the study (< 80% or > 120% measured by pill counts), then they should be discontinued from the study.

9.5 EFFICACY AND SAFETY VARIABLES

9.5.1 Diagnostic and Efficacy Assessments

9.5.1.1 Diagnostic Assessment

Mini International Neuropsychiatric Interview (Version 7.0.0, 01 Jan 2014)

The MINI (Version 7.0.0, 01 Jan 2014) is a clinician-rated diagnostic assessment that will be considered a source document in this study. The interview will be administered by the PI or Sub-Investigator who is a psychiatrist or a doctoral-level clinical psychologist or who has extensive professional training and experience in the diagnosis of mental illness.

9.5.1.2 Primary Efficacy Assessment

[figure not shown]
Montgomery-Asberg Depression Rating Scale

The MADRS (Montgomery and Åsberg, 1979) is a 10-item, clinician-rated scale that evaluates the patient's depressive symptomatology during the past week. Patients are rated on items assessing feelings of sadness, lassitude, pessimism, inner tension, suicidality, reduced sleep or appetite, difficulty in concentration, and lack of interest. Each item will be scored on a 7-point scale with a score of 0 reflecting no symptoms and a score of 6 reflecting symptoms of maximum severity. This scale will be administered by a trained rater with adequate experience in the assessment of the patient's depressive symptomatology using the MADRS.

9.5.1.3 Secondary Efficacy Assessment

Clinical Global Impressions-Severity

The CGI-S (Guy, 1976) is a clinician-rated scale that measures the overall severity of a patient's illness in comparison with the severity of other patients the physician has observed. The patient is rated on a scale from 1 to 7 with 1 indicating a "normal state" and 7 indicating "among the most extremely ill patients." The CGI-S will be administered by the PI or a Sub-Investigator with extensive professional training and experience in assessing mental illness.

9.5.2.1 Adverse Events

An AE is any untoward medical occurrence in a patient or clinical investigation patient administered a pharmaceutical product and which does not necessarily have to have a causal relationship with this treatment. An AE can therefore be any unfavorable and unintended sign (including an abnormal laboratory finding, for example), symptom, or disease temporally associated with the use of a medicinal product, whether or not considered related to the medicinal product (ICH-E2A).

For the purpose of the site's data collection responsibilities, any untoward event that was reported from the time the patient signed the ICF until 30 days after the final protocol-defined study visit or, if the final visit does not occur, the last known dose of investigational product, is to be considered an AE.

Examples of AEs are as follows:

- Changes in the general condition of the patient
- Subjective symptoms offered by or elicited from the patient
- Objective signs observed by the Investigator or other study site personnel
- All diseases that occur after signing inform consent, including any change in severity or frequency of preexisting disease
- All clinically relevant abnormalities in laboratory values or clinically relevant physical findings that occur during the study schedule

Please note medical procedures scheduled prior to consenting, but occurring during the study should not be captured as AEs, but should be listed in the medical history if related to a pre-existing condition.

9.5.2.2 Causality Assessment

For each AE, the Investigator must provide an assessment of causal relationship to the investigational product. The causality assessment must be recorded on the appropriate AE reporting page of the patient's eCRF. Causal relationship must be assessed by answering the following question:

Is there a reasonable possibility the investigational product caused the event?

Yes: There is evidence to suggest a causal relationship between the investigational product and AE; i.e.:

- There is a reasonable temporal relationship between the investigational product and the event, and/or
- The event is unlikely to be attributed to underlying/concurrent disease, other investigational products, or other factors, and/or
- Positive dechallenge and/or rechallenge exist

No: There is no evidence to suggest a causal relationship between the investigational product and AE, i.e.:

- There is no reasonable temporal relationship between the investigational product and the event, or
- The patient did not take the investigational product, or
- The event is likely to be attributed to underlying/concurrent disease, other investigational products, or other factors, or
- The event is commonly occurring in the (study) population independent of investigational product exposure

9.5.2.3 Severity Assessment

The Investigator will provide an assessment of the severity of each AE by recording a severity rating on the appropriate AE reporting page of the patient's eCRF. *Severity*, which is a description of the intensity of manifestation of the AE, is distinct from *seriousness*, which implies a patient outcome or AE-required treatment measure associated with a threat to life or functionality (Section 9.5.2.4). Severity will be assessed according to the following scale:

Mild: A type of AE that is usually transient and may require only minimal

treatment or therapeutic intervention. The event does not generally

interfere with usual activities of daily living.

Moderate: A type of AE that is usually alleviated with additional specific therapeutic

intervention. The event interferes with usual activities of daily living, causing discomfort but poses no significant or permanent risk of harm to

the research participant.

Severe: A type of AE that interrupts usual activities of daily living, or significantly

affects clinical status, or may require intensive therapeutic intervention.

9.5.2.4 Serious Adverse Events

An SAE is any untoward medical occurrence that at any dose:

- Results in death
- Is life threatening
- Requires inpatient hospitalization or prolongation of existing hospitalization

- Results in persistent or significant disability/incapacity, or
- Is a congenital anomaly/birth defect

Important medical events that may not result in death, be life threatening, or require hospitalization may be considered serious when, based on appropriate medical judgment, they may jeopardize the patient or subject and may require medical or surgical intervention to prevent one of the outcomes listed in this definition. Examples of such medical events include allergic bronchospasm requiring intensive treatment in an emergency room or at home, blood dyscrasias or convulsions that do not result in patient hospitalization, or the development of investigational product dependency or drug abuse.

Emergency room visits that do not result in hospitalization should be evaluated for one of the other serious outcomes to determine whether they qualify as SAEs.

Preplanned hospitalizations (e.g., elective procedures for preexisting conditions that did not worsen, such as cosmetic surgery and hysterectomy) or routine (i.e. required) country-specific hospitalization during washout are excluded from SAE reporting.

9.5.2.5 Reporting Adverse Events and Serious Adverse Events

At each visit, patients are to be queried regarding any AEs or SAEs that have occurred since the previous visit. Patients will be asked to volunteer information with a nonleading question such as, "How do you feel since your last visit?" Study site personnel will record all pertinent information in the patient's eCRF.

All AEs must be recorded on the appropriate AE reporting page of the patient's eCRF whether or not they are considered causally related to the investigational product.

For every AE, the Investigator must:

- Provide an assessment of the seriousness of the event (i.e., is it an SAE?), as well as the severity and casual relationship
- Document all actions taken with regard to the investigational product
- Detail any other treatment measures taken for the AE
- Document the outcome of the AE

In addition, patients are to be reminded, as described in the ICF and in accordance with Section 9.5.2.1, to notify site personnel of any AEs occurring during the 30 day post-study period. Any AEs reported by the patient (or patient representative) during this period are to be recorded in original source documents. AEs are also to be recorded in the eCRF if at least one of the following conditions is met: 1) the event meets the criteria for an SAE (see Sections 9.5.2.4 and 9.5.2.6), and/or 2) the event is judged by the Investigator to be potentially causally related to investigational product.

Any AEs that are ongoing at the time of the final protocol-defined study visit will be followed until the condition returns to prestudy status, has resolved or stabilized, or can be explained as being unrelated to the investigational product. If a follow-up visit is deemed necessary for appropriate safety surveillance, it will take place within 30 days of the final protocol-defined study visit.

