Study RGH-MD-56 was 11 weeks in duration and comprised up to 14 days of screening followed by 8 weeks of double-blind treatment and 1 week of safety follow-up. A total of 584 bipolar I patients were randomized to 1 of 4 treatment groups and 578 patients received at least 1 dose of the investigational product: placebo (n = 145), cariprazine 0.75 mg/day (n = 141), cariprazine 1.5 mg/day (n = 146), cariprazine 3 mg/day (n = 146). Overall, 72.5% of the patients completed the study: 72.4% in the placebo group, 73.0% in the cariprazine 0.75 mg/day group, 80.1% in the cariprazine 1.5 mg/day group, and 64.4% in the cariprazine 3 mg/day group. The average patient age was 42 years, and approximately 62% were female. For both the primary and secondary efficacy parameters, change from baseline in MADRS total score and Clinical Global Impressions-Severity (CGI-S) score at Week 6, statistically significant improvement was demonstrated for the cariprazine 1.5 mg dose relative to placebo. Nominally significant improvement was shown for cariprazine 3 mg, which did not remain statistically significant after adjusting for multiplicity. No statistically significant treatment effect was shown for the 0.75 mg dose at Week 6. A post-hoc analysis of patients who completed the full 8 weeks of treatment (completer population) in Study RGH-MD-56 demonstrated similar reductions from baseline relative to placebo in MADRS total score for the cariprazine 1.5 and 3 mg/day groups at Week 6 and Week 8. Cariprazine was generally well-tolerated. No deaths were reported during the study. Serious adverse events were reported for 5 patients (3.4%) in the placebo group, 1 patient (0.7%) in the cariprazine 0.75 mg group, and 2 patients (1.4%) each in the cariprazine 1.5 mg and 3 mg treatment groups. Adverse events that led to discontinuation were reported in similar proportions of patients across the placebo (10.3%) and cariprazine (8.2%-11.6%) treatment groups. The most common AEs that led to discontinuation were akathisia, agitation, anxiety, and depression. Overall, TEAEs were reported for 55% of patients in the placebo treatment group and 57%-62% of patients in the cariprazine treatment groups. Akathisia and irritability were the only TEAEs reported for $\geq 5\%$ of patients in any cariprazine treatment group and at an incidence at least twice that of the placebo group.

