9.5.2.6 Immediate Reporting of Serious Adverse Events and Events of Special Interest

The Sponsor is required to inform worldwide regulatory authorities of SAEs and Ocular Events of Special Interest that meet specific criteria. Therefore, the Sponsor must be notified immediately regarding any SAE and Ocular Events of Special Interest that occur after informed consent is obtained.

The following serious and non-serious adverse events (ie, Ocular Events of Special Interest) require a 15-day alert report:

- cataract, lens, or lenticular abnormality or change, opacity, opacification or opalescence
- blindness, night blindness, visual acuity or vision decrease, abnormality or change, visual acuity test abnormality or change
- retinal, macular, or optic nerve degeneration, abnormality or change; retinal pigment epithelium detachment, abnormality or change
- color vision decrease, abnormality or change

Within 24 hours of learning of any AE that meets one of the criteria for an SAE, the study site personnel must report the event to the Sponsor's Global Drug Safety department on the SAE Form for Clinical Trials.

Within 24 hours of learning of any non-serious Ocular Event of Special Interest, the study site personnel must report the event on the Ocular Event Reporting Form. Serious Ocular Events should be reported on the SAE Form for Clinical Trials.

In addition to completing the appropriate form, the Sponsor's Study Safety Physician may also be notified by telephone.

If, during follow-up, any nonserious AE worsens and eventually meets the criteria for an SAE, that AE should be recorded as a new SAE.

The site must transmit the SAE Form for Clinical Trials or the Ocular Event of Special Interest form to the SAE fax number shown below. Even if an initial report is made by telephone, the SAE Form for Clinical Trials or the Ocular Event of Special Interest form, completed with all available details, must still be faxed within 24 hours of knowledge of the event at the study site.

Supplemental information should be submitted as soon as available and may include laboratory results, radiology reports, progress notes, hospital admission and emergency room notes, holding and observation notes, discharge summaries, autopsy reports, and death certificates.

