5.1.1.4.2 Adverse Events

The following adverse event (AE) terms are defined:

Table 5-16 AE Terms

Term	Description
Treatment-emergent	An event that initially occurs or increases in severity on or after the treatment start date, where: 
 Treatment start date \leq event start date \leq treatment end date + 30
Newly-emergent	An AE occurring during the safety follow-up period will be considered a newly emergent adverse event if the AE was not present before the start of the safety follow-up period or was present before the start of the safety follow-up period and increased in severity during the safety follow-up period.
On-therapy	An event where: 
 Treatment start date \leq event start date \leq treatment end date + 30

AEs, encompassing abnormalities and surgeries reported as occurring after the Screening Visit, will be coded using MedDRA version 19.1 or newer. Unique patients reporting AEs in the following AE categories will be summarized by treatment group for the Safety Population as follows:

[figure not shown]
Table 5-17**AE Summaries**

Parameter	Description	Timing	Methodology
Overall summary	Overall summary only for the following categories: 
 • Deaths • Treatment-emergent AEs (TEAEs) • On-therapy Serious adverse events (SAEs) • AEs leading to discontinuation 	Double-blind Treatment Period	Categorical descriptives
	Overall summary only for the following categories: 
 • Deaths • Serious adverse events (SAEs) • Newly emergent AEs 	During the Safety Follow-up Period and within 30 days after the last dose of double-blind treatment	Categorical descriptives
TEAEs	Overall summary and by SOC and PT	Double-blind Treatment Period	Categorical descriptives
NEAEs	Overall summary and by SOC and PT	During the Safety Follow-up Period and within 30 days after double-blind treatment	Categorical descriptives
Common TEAEs	Summary by SOC, PT, sorted by decreasing frequency for the test treatment 
 • Includes TEAEs occurring in $\geq 2.0\%$ of participants in any treatment group. Event rates will not be rounded prior to comparison with the 2.0% cutpoint. Summary by PT, sorted by decreasing frequency for the test treatment	Double-blind Treatment Period	Categorical descriptives

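### Non-serious AEs reach the eCRF after the final visit only if judged related, but the SAP's off-drug AE windows run to 30 days after treatment with no allowance for this

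*Protocol*

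**What the plan says.** **Recording rule.** Protocol 9.5.2.5 requires AEs to be entered in the eCRF "whether or not they are considered causally related to the investigational product". For the 30-day post-study period the same section sends reported AEs to source documents and adds a restriction: "AEs are also to be recorded in the eCRF if at least one of the following conditions is met". The conditions are that "the event meets the criteria for an SAE" and/or that "the event is judged by the Investigator to be potentially causally related to investigational product". Patients are reminded to notify the site in this period; no routine contact is described.

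**Collection window.** Protocol 9.5.2.1 counts untoward events "until 30 days after the final protocol-defined study visit or, if the final visit does not occur, the last known dose of investigational product". Protocol 9.1 gives one week of off-drug safety follow-up, and Protocol 9.7.2 treats a patient as having entered it if Visit 7 (Week 7) took place.

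**Analysis windows.** SAP Table 5-16 defines treatment-emergent and on-therapy events up to treatment end plus 30 days. It defines newly emergent AEs as those arising or worsening in the safety follow-up period. SAP Table 5-17 times the newly emergent AE summary, overall and by SOC and PT, as "During the Safety Follow-up Period and within 30 days after double-blind treatment". The TEAE, causality and ocular rows of that table are timed to the double-blind treatment period.

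**Ocular events.** Protocol 9.5.2.6 has no causality condition: "Within 24 hours of learning of any non-serious Ocular Event of Special Interest, the study site personnel must report the event".

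**The concern.** The analysis window ends inside the collection window, so the end date is not the problem. What changes is the rule for what is captured within it. Part of the off-drug period has every AE; the rest has only SAEs and events judged related. A newly emergent AE table that covers both parts reads as one count over one period when it is not.

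The omitted events are not a random subset. Protocol 9.5.2.2 directs a causality answer of no when timing does not fit, when underlying disease or other factors are the likely cause, or when the event is common in the population. After drug is stopped, with standard treatment permitted (Protocol 9.1), those grounds readily apply to late-onset and psychiatric events.

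The point where the rule switches also depends on attendance at Visit 7. Off-drug non-serious AE rates would therefore be understated, and more so for patients who leave and do not return. A smaller consequence is that a post-study ocular event of special interest that is non-serious and judged unrelated must be reported on its own form but need not be in the eCRF, so the two sources need not agree.

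**Working it through.** The plan states no figure for the filtered share, so there is none to reproduce.

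**Inputs**
- Analysis window: 30 days after treatment end (SAP Tables 5-16 and 5-17).
- Follow-up: 7 days, ending at Visit 7 (Protocol 9.1, 9.7.2).
- Last scheduled dose: Day 42 (Protocol Table 9.4.5–1), so Visit 7 is nominally Day 49.
- g: days from last dose to Visit 6/ET. Protocol 9.3.3 allows for g above 4.
- Assumption: Visit 7 falls 7 days after Visit 6/ET.

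**Completer, g = 0.** The analysis window ends on Day 42 + 30 = Day 72, and collection continues to Day 49 + 30 = Day 79. Fully recorded: 49 − 42 = 7 days. Filtered: 72 − 49 = 23 days; 23/30 = 76.7%.

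**Visit 7 attended, general g.** Filtered share = (30 − g − 7)/30.

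| g | Filtered days | Share |
|---|---|---|
| 0 | 23 | 76.7% |
| 1 | 22 | 73.3% |
| 4 | 19 | 63.3% |
| 7 | 16 | 53.3% |
| 8 | 15 | 50.0% |

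Most of the window is filtered unless Visit 6/ET comes 8 or more days after the last dose.

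**Visit 7 missed.** Two readings are possible.
- If the post-study period starts at the last dose, as Protocol 9.5.2.1 suggests, the share is 30/30 = 100%.
- If AEs elicited at Visit 6/ET count as fully recorded, it is (30 − g)/30: 29/30 = 96.7% at g = 1 and 26/30 = 86.7% at g = 4.

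**Across patients.** Let m be the share missing Visit 7, with g = 0. Filtered person-day share = [30 − 7(1 − m)]/30.
- m = 0: 23/30 = 76.7%.
- m = 22%, the planned dropout rate (Protocol 9.7.9), assuming every dropout misses Visit 7: (30 − 5.46)/30 = 81.8%.

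**Between arms (illustration only).** Protocol 7.0 reports completion in RGH-MD-56 of 72.4% on placebo and "80.1% in the cariprazine 1.5 mg/day group, and 64.4% in the cariprazine 3 mg/day group". Non-completion was therefore 27.6%, 19.9% and 35.6%. If non-completers, and only they, can miss Visit 7, m lies between 0 and those values. At the upper limit the formula gives:
- placebo: (30 − 5.068)/30 = 83.1%
- 1.5 mg: (30 − 5.607)/30 = 81.3%
- 3 mg: (30 − 4.508)/30 = 85.0%

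The widest gap is 85.0 − 81.3 = 3.7 percentage points. That study treated for 8 weeks and this one treats for 6, so the rates do not carry over directly.

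**The case against.** The strongest objection is that the SAP may never use the filtered days. Every TEAE row of Table 5-17 is timed to the double-blind treatment period, and Table 5-16 ties newly emergent AEs to the safety follow-up period, which is one week and fully recorded. The joint timing in Table 5-17 can be read as requiring both conditions. Much of SAP Section 6, including the visit definitions, is blacked out, so only the visible text can be judged.

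This limits the point but does not remove it. The TEAE definition still runs to 30 days, and the newly emergent AE timing can equally be read as extending to 30 days. The overall and SAE rows use the same kind of phrase for reporting to 30 days after the last dose. A programmer could implement either reading.

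Four stronger inferences might tempt a reader, and the documents do not support them:
- **The causality table is distorted.** The only causality summary shown is for TEAEs in the double-blind period; newly emergent AEs are not split by causality.
- **The whole window is always filtered without Visit 7.** The last-dose anchor in Protocol 9.5.2.1 fixes where collection ends. It does not say that full recording stops at last dose, and discontinuers should have a Visit 6/ET at which AEs are queried.
- **The arm with most dropout will look safer off drug.** Visit 7 attendance by arm is not given, discontinuers are meant to be followed for another week, and only non-serious events judged unrelated are lost.
- **Ocular events are lost.** They reach the sponsor on a dedicated form, and the SAP ocular summary is timed to the double-blind period.

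It is also fair that reporting after Visit 7 is passive. Removing the causality filter would not make that period comparable with the first week.

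**Conclusion.** The mismatch is real. If the 30-day windows are applied as written, non-serious off-drug counts combine about 7 fully recorded days with about 23 filtered days (77%) for a completer seen at Visit 7. The filtered share is about 87% to 100% if Visit 7 is missed and any Visit 6/ET falls within 4 days of the last dose. These figures assume nominal visit timing.

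The newly emergent AE summary is the table most exposed. The TEAE tables are exposed only if the definition prevails over the row timing, and the SAP must settle which does. SAEs and deaths are recorded whatever the causality and are unaffected, as are the efficacy analyses. The size of any imbalance between arms cannot be determined from the documents. The ocular point concerns reconciliation of two data sources, not missing safety reports.

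**What to change.** **Preferred, in the SAP.** End tabulation of non-serious TEAEs and newly emergent AEs at the last fully recorded visit: Visit 7, or Visit 6/ET if Visit 7 is missed. Report deaths and SAEs to 30 days. List later non-serious events separately, labelled as captured only when judged related. Show beside the table the number per arm with Visit 7, which Protocol 9.7.2 already plans to count. The cost is SAP wording and table shells.

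**Alternative, in the protocol.** Amend 9.5.2.5 so that every AE already in source documents with onset up to 30 days after last dose enters the eCRF, whatever its causality and whether or not Visit 7 took place. State in the SAP that reporting after Visit 7 is patient-volunteered. The cost is an amendment and slightly more data entry; active follow-up is not created.

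**In either case:**
- Reconcile the 30-day TEAE definition in Table 5-16 with the double-blind timing of the TEAE rows in Table 5-17.
- State whether the newly emergent AE window is the follow-up week or 30 days.
- Add ocular events of special interest as a third eCRF condition in 9.5.2.5, so that the forms and the eCRF agree.
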